## 10.2. Handling of Missing Data

### 10.2.1. Adverse Events Severity and Relationship to Study Drug

AEs with severity not reported will be counted as severe, and AEs with relationship to study drug not reported will be counted as related.

### 10.2.2. Missing Start and Stop Dates for Adverse Events

Missing start date and times will be handled as follows:

- AE onset date completely missing:
  - If AE is not ongoing and AE onset date missing and AE end date missing, then impute AE onset as date/time of first dose.
  - Else if AE is not ongoing and AE onset date missing and AE end date not missing and date/time of first dose  $\leq$  AE end date, then impute AE onset as date/time of first dose of study drug.
  - Else if AE is not ongoing and AE onset date missing and AE end date not missing and AE end date is BEFORE first dose of study drug, then impute AE onset as AE end date YEAR and MONTH with 01 as the day and 00:00 as time.
  - Else if AE IS ongoing and AE onset date missing, then impute AE onset as date/time of first study drug dose.
- AE onset date has year and month only:
  - If AE onset date has year and month only and they are the year and month of first dose of study drug, then impute AE onset as date/time of first dose:
  - Else if AE onset date has year and month only and date/time of first dose is not missing, then impute AE onset as AE onset year and month with 01 as the date and 00:00 as the time.
- AE onset date has year only:
  - If AE onset date has year only and it is year of first dose of study drug, then impute AE onset as date/time of first dose of study drug.
  - Else if AE onset date has year only and date of first study drug dose is not missing and year of AE onset is NOT the year of first dose of study drug, then impute AE onset as Jan. 1 of the AE onset year and 00:00 as the time.
- AE onset missing (where it was not handled by the above cases):

- If AE onset date is missing, then impute AE onset as date/time of first study drug dose.
- AE onset has complete date but missing time:
  - If AE onset date is a date only and is same as date of first study drug dose, then impute AE onset as date/time of first study drug dose.
  - Else if AE onset date is a date only and is NOT = date of first study drug dose, then impute AE onset as AE onset date with 00:00 as the time.

Missing end date and times will be handled as follows:

- AE end date - completely missing:
  - If AE is not ongoing and both AE onset and AE end dates are missing, then impute AE end date as date/time of last study drug dose.
  - Else if AE is not ongoing and AE onset date not missing and AE end date missing AND AE onset date  $\leq$  date/time of last dose, then impute AE end date as date/time of last study drug dose.
  - Else if AE is not ongoing and AE onset date is not missing and AE end date is missing and date of last dose is not missing and AE onset is AFTER date of last dose, then impute AE end date as the last day of the month of AE onset date, with 23:59 as time.
- AE end date = year and month only:
  - If AE is NOT ongoing and AE end date consists of year and month only, then impute AE end date as the last day of the month of AE end date month and year, with 23:59 as time.
- AE end date = year only:
  - If AE is NOT ongoing and AE end date consists of a year only, and year = year of AE onset and AE onset date  $\leq$  date of last study drug dose, then impute AE end date as the date of last study drug dose.
  - Else if AE is NOT ongoing and AE end date consists of a year only, and year = year of AE onset and AE onset date  $>$  date of last study drug dose, then impute AE end date as the year and month of AE onset, with the last day of the month as the day, and 23:59 as the time.
- AE end date = complete date but no time:
  - If AE is NOT ongoing and AE end date consists of a complete date but no time, then impute AE end date = trim (AE end date) || "T23:59".

### 10.2.3. Missing Start and Stop Dates for Medications

To determine whether medications were used before dosing started and whether they were used after dosing started, missing or partial dates for medications will be imputed according to the following rule:

Missing medication start date/time:

- If only have a YEAR, impute as Jan. 1, at one minute after midnight.
- Else if only have YEAR and MONTH, impute as Day 1 of month, at one minute after midnight.
- Else if have a complete date, impute TIME as one minute after midnight.
- Else if completely missing, and ((end date is present and  $\geq$  date of first dose) or (end date is missing and is marked as “ONGOING”)), impute as date and time of first dose. If missing and end date/time is present and prior to date of first dose, then leave as missing.

Missing medication end date/time:

- If only have a YEAR and it is same as year of study completion, impute as date of study completion with time of 23:59.
- Else if only have a YEAR, impute as December 31 with time of 23:59.
- Else if only have YEAR and MONTH, then impute to last day of the month, with time of 23:59.
- Else if have a complete date but no time, impute time of 23:59.
- Else if end date/time completely missing and not flagged as Ongoing, impute as date of study completion with time of 23:59.

Otherwise missing, no imputation.

### 10.2.4. Laboratory Data

For laboratory data, a missing baseline value will be replaced with the last available assessment. A retest value will be used if the first test result is invalid, e.g., specimen hemolyzed.

Laboratory data that are continuous in nature but are less than the lower limit of quantitation/limit of detection (LOD) will be imputed as follows:

- A value that is 1 unit less than the LOD will be used for calculation of descriptive statistics if the data are reported in the form of “ $< x$ ” ( $x$  is considered as the LOD). More specifically,  $x-1$  is used for data summarization if the data are reported in the form “ $< x$ ”; and  $x.e$  where  $e = d-1$  will be used for analysis if the data are reported in the form “ $< x.d$ ”.
- The LOD will be used for calculation of descriptive statistics if the data are reported in the form “ $\leq x$ ” or “ $\geq x$ .”

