## **8. STATISTICAL CONSIDERATIONS**

### **8.1. General Considerations**

All individual data will be listed as collected. All statistical summaries and analyses will be performed using [REDACTED]

Continuous data will be summarized using an 8-point descriptive summary (n, mean, standard deviation, median, interquartile range (IQR) [25% quartile, 75% quartile]), minimum, and maximum value unless otherwise stated.

Categorical data will be summarized using the counts and percentages.

For analysis, Day 1 is defined as the day of the first study drug dose. The preceding day is Day -1.

Baseline is the last assessment (scheduled or unscheduled) obtained before start of study drug dosing, unless otherwise specified in the SAP.

Any changes to the protocol-specified analyses will be pre-specified in the Statistical Analysis Plan prior to data lock.

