### **6.2. Baseline Definition**

In general, assessments obtained at Study 0170 Visit 9, which coincides with Study 0171 Visit 1, will serve as the baseline assessment for Study 0171. Subjects will start taking Study 0171 study drug on the day after Visit 1. If the start of Study 0171 dosing is delayed, however, the latest assessment obtained before the first Study 0171 dose will be used, even if obtained after Visit 1.

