### **6.3.3. Change from Baseline**

Change from baseline is calculated as postbaseline result – baseline result. If either the baseline or the postbaseline result is missing, change values are treated as missing.

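### Some imputation rules in SAP 10.2 give wrong values if programmed as written; the effect is confined to descriptive safety output and probably few records

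*SAP*

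**What the plan says.** **AE onset (SAP 10.2.2).** For an onset with year and month only, if "they are the year and month of first dose of study drug, then impute AE onset as date/time of first dose". The year-only branch is parallel, again with first dose supplying the imputed value: "If AE onset date has year only and it is year of first dose of study drug, then impute AE onset as date/time". Neither looks at the AE end date. The branch for a completely missing onset does: an AE that ended before first dose is given the first day of its end month.

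**AE end (SAP 10.2.2).** If only the end year is known, it equals the onset year, and onset is not after last dose, "then impute AE end date as the date of last study drug dose".

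**Results below the limit (SAP 10.2.4).** "A value that is 1 unit less than the LOD will be used for calculation of descriptive statistics". For decimals, a result reported as `<x.d` becomes x.e with e equal to d minus 1. The list closes with forms that take the limit itself, one of which is `≥ x`.

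**Laboratory baseline (SAP 10.2.4).** "a missing baseline value will be replaced with the last available assessment". On baseline in general, SAP 6.2 says that if dosing is delayed "the latest assessment obtained before the first Study 0171 dose will be used, even if obtained after Visit 1". Protocol 8.1 says: "Baseline is the last assessment (scheduled or unscheduled) obtained before start of study drug dosing, unless otherwise specified in the SAP". SAP 6.3.3 adds: "If either the baseline or the postbaseline result is missing, change values are treated as missing".

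**The concern.** Imputation rules are normally coded literally, and several of these, coded literally, contradict the recorded data or the rule's own purpose. An event known to have ended before dosing can enter the treatment-emergent (TEAE) tables. A result below a limit can be summarised as above it. An end date can land in a year that the site did not record. The laboratory baseline rule leaves out the one restriction that makes a value a baseline.

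Safety is the primary objective. After early termination, SAP section 5 plans a single analysis after lock, so no later planned analysis would correct a derivation error.

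**Working it through.** The plan gives no figure to reproduce. Each rule was applied as written to worked cases. The dates and reporting formats below are assumed for illustration; the documents give neither.

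**(a) Partial AE onset.** Assume first dose on 15 March 2021.
- Onset March 2021, end 5 March 2021: the month matches, so onset becomes 15 March, after the end.
- Onset 2021, end 10 February 2021: the year matches, so onset becomes 15 March, again after the end.
- SAP 8.1 counts an AE as treatment-emergent if it starts from first dose through 14 days after last dose. Both events would therefore be TEAEs.
- End days that produce this: 1 to 14 March for a month-only onset, 14 of 31; 31 + 28 + 14 = 73 of 365 for a year-only onset. These show the reach of the rule, not how often it will be met.
- Exposed records: protocol 6.4.3.2 sends AEs between consent and first dose to the Study 0170 database, and protocol 7.1.1 sends conditions with onset before first dose to medical history. However, SAP 8.1 says AEs are collected from consent and plans a listing of non-treatment-emergent AEs, and SAP 6.2 foresees delayed dosing. Dosing starts the day after Visit 1, so the window is about one day unless dosing is delayed.
- Possible consequence: if all 110 enrolled subjects were dosed, the SAP 8.1 table of terms above 3% turns on 3/110 = 2.7% versus 4/110 = 3.6%, so one subject can move a term across the line.

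**(b) Results below the limit.** Literal reading: d is an integer and e = d − 1. Alternative: subtract one unit in the last reported decimal place.

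| Reported | Literal | Last decimal place |
|---|---|---|
| `<0.5` | 0.4 | 0.4 |
| `<0.25` | 0.24 | 0.24 |
| `<5.0` | e = −1, undefined | 4.9 |
| `<0.10` | 0.9 (9 times the limit) | 0.09 |
| `<0.05` | 0.4 | 0.04 |
| `<1.10` | 1.9 | 1.09 |

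Of the 99 two-decimal limits from 0.01 to 0.99, nine (0.02 to 0.10) give a literal value above the limit. The opening sentence does not say which unit is meant either: a whole unit off 0.10 gives −0.90. The form `≥ x` sits under a rule introduced for values below the limit, and `> x` has no rule.

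**(c) Laboratory baseline.** SAP 6.2 ties baseline to Study 0170 Visit 9 (Study 0171 Visit 1). If that sample is missing, an earlier Study 0170 value would be a natural replacement and would satisfy protocol 8.1. SAP 10.2.4 neither says this nor refers back to 6.2. The scheduled post-baseline samples are at Week 10, Week 26 and early termination, and nothing in 10.2.4 excludes them.

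**(d) Year-only AE end.** Assume onset 10 November 2020, end 2020, last dose 1 September 2021. The years match and onset precedes last dose, so the end becomes 1 September 2021. The latest date consistent with the record is 31 December 2020, so the imputed end is 243 + 1 = 244 days too late. For medications, SAP 10.2.3 sets a year-only end to 31 December, or to study completion if that falls in the same year. TEAE status depends on onset, and no AE summary listed in SAP 8.1 uses the end date.

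**The case against.** The strongest case is that these are drafting points that a competent programmer would resolve. The exposed window in (a) is about one day, and the error over-counts TEAEs, in line with SAP 10.2.1, which counts unreported severity as severe. In (b) the governing sentence is one unit below the limit, with the decimal formula as illustration. In (c) the pre-dose meaning is clear from SAP 6.2 and protocol 8.1. In (d) no table changes. Much of this stands and keeps the point small. It does not remove it: (a) and (d) involve no ambiguity, and in (b) the explicit formula is what would be coded.

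Three stronger readings are tempting but not supported:
- *A reader might infer that 10.2.4 conflicts with 6.3.3.* It does not. A baseline that has been replaced is no longer missing, so 6.3.3 then computes the change.
- *A reader might infer that the plan makes on-treatment values the baseline.* With ALT of 60 at Week 10, 120 at Week 26 and no baseline, using the last value gives changes of 60 − 120 = −60 and 120 − 120 = 0, a rise shown as a fall. That needs a programmer to override both definitions of baseline. The text permits it by omission but does not intend it.
- *A reader might infer that many pre-dose events will enter the TEAE tables.* Protocol 6.4.3.2 and 7.1.1 keep most of them out of the Study 0171 AE data.

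**Conclusion.** The point holds as a minor one. Rules (a), (b) and (d) give wrong or undefined values for identifiable inputs if coded as written. Rule (c) is a missing restriction whose intent is fairly clear. All analyses are descriptive and no hypothesis test is involved. Rule (a) can change TEAE counts, (b) and (c) can change laboratory summaries, and (d) affects listings only.

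The number of affected records is not in the documents; that it is small is a judgement from the protocol's AE recording rules. Item (b) also rests on assumed reporting formats and on reading the decimals as an integer. The content of protocol 8.6 on missing data is redacted, so it cannot be checked for further guidance.

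**What to change.** - **10.2.2, partial onset.** In both branches add: if the AE end date is before first dose, impute onset as the first day of the recorded month (year-month) or 1 January of the recorded year (year-only). In the examples this gives 1 March and 1 January 2021, both before the end date and not treatment-emergent. A bare exception clause is not enough. The alternative in the year-only branch applies only when the onset year differs from the first-dose year, so the record would match no rule or fall to the catch-all, which imputes first dose again.
- **10.2.4, limits.** Replace the decimal formula with subtraction of one unit in the last reported decimal place. Put `≥ x`, and `> x` if the laboratory reports it, on a separate line for upper limits using x. This keeps the SAP's own one-unit approach; half the limit would be a preference, not a correction.
- **10.2.4, baseline.** Specify the last valid assessment before the first Study 0171 dose; if there is none, baseline and change are missing.
- **10.2.2, year-only end.** Cap the imputed date at 31 December of the recorded year, on the model of SAP 10.2.3.

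The cost is four short SAP edits and small derivation changes before lock. No data collection changes.
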